1.3.2. STUDY VARIABLES

	Screening	C1	C2	C3	C4	C5 to PD	EOT	Up to EOS
Week	-4 To -1	0	Q3w ±3 days unless dosing needs to be held for toxicity reasons					
Day	-28 To -1	1 ^a	Q21 Days ±3 days unless dosing needs to be held for toxicity reasons					
Informed Consent								
Informed Consent ^b	X							
Consent and Collection of Specimens for Future Biomedical Research	X							
Study Procedures								
Medical History	X							
Physical Exam (Full)	X							
Targeted Physical Exam (Based On Symptoms)		X	X	X	X	X	X	
Vital Signs ^c	X	X	X	X	X	X	X	
ECG ^d	X	As clinically indicated					X	
Prior and Concomitant Medications	<----->							
Demography, Including Baseline Characteristics And Tobacco Use	X							
Eligibility Criteria	X							
Laboratory Assessments								
Clinical Chemistry ^e	X	X ^f	X	X	X	X	X	
Hematology ^e	X	X ^f	X	X	X	X	X	
TSH ^g (Reflex Free T3 Or Free T4 ^h)	X	X	X	X	X	X	X	
Hepatitis B, C and HIV ⁱ	X							
Urinalysis	X						X	
Pregnancy Test ^j	X	if clinically indicated						
Monitoring								
ECOG Performance Status	X	X	X	X	X	X	X	
AE/SAE/AESI Assessment ^k		X	X	X	X	X	X	
Post-treatment Follow-up ^l								X

Sponsor: Grupo Español de Tumores Neuroendocrinos y Endocrinos (GETNE)

IMPs Administration						
Cabozantinib ^m		X (p.o. daily, until PD or unacceptable toxicity)				
Atezolizumab ^m		X	X	X	X	X
Biological samples collection						
Tumor Biopsy (Archival, If Available)	(X)					
Processed blood samples ⁿ	X		X			X
Efficacy Evaluations						
Tumor evaluation (CT scan or MRI) (RECIST 1.1) ^o	X	q12w ± 1w until confirmed objective disease progression/death (whichever comes first).			(X)	
Note: all assessments on treatment days are to be performed prior to atezolizumab infusion, unless otherwise indicated. C: cycle; ECG: electrocardiogram; IM: intramuscular; LFT: liver function test; QxW: every x weeks; T3: triiodothyronine; T4: thyroxine; TSH: thyroid-stimulating hormone. EOT: end of treatment, EOS: end of study.						

- a) Every effort should be made to minimise the time between inclusion and start of treatment. (i.e. within 1 day of inclusion)
- b) Informed consent of study procedures may be obtained prior to the 28-day screening window. If laboratory or imaging procedures were performed for different reasons prior to signing consent, these can be used for the screening purposes with the consent of the patient. However, all screening laboratory and imaging results must have been obtained within 28 days of inclusion.
- c) Body weight is to be recorded at each visit along with vital signs.
- d) Any clinically significant abnormalities detected require triplicate ECG results.
- e) Complete blood count that includes total white blood cell count with leukocyte formula, haemoglobin, and platelet count. The analytical studies may be performed up to 72 hours before the scheduled visits in order to have the results at the time of the patient's visit. Biochemistry tests include albumin, alkaline phosphatase, lactate dehydrogenase (LDH), calcium, magnesium, phosphorus, sodium, potassium, creatinine, creatine kinase, direct bilirubin, indirect bilirubin, total bilirubin, total protein, urea, uric acid, amylase, lipase, and glucose tests. Liver test panel function include alanine transaminase (ALT), aspartate transaminase (AST), alkaline phosphatase (ALP), and gamma-glutamyl transpeptidase (GGT) tests. Tests for pancreatic enzymes include lipase, protease, amylase, and trypsinogen tests.
- f) If clinical chemistry screening and haematology assessments are performed within 3 days prior to day 1 (first infusion day), they do not need to be repeated at day 1.
- g) If TSH is measured within 14 days prior to C1D1 (first infusion day), it does not need to be repeated at day 1.
- h) Free T3 or free T4 will only be measured if TSH is abnormal or if there is clinical suspicion of an AE related to the endocrine system.
- i) Serology including HIV, hepatitis B (HBsAg and anti-HBc), and hepatitis C virus (HCV).
- j) Women of childbearing potential are required to have a pregnancy test within 72 hours prior to the first dose of the study drug, and every 3 cycles (9 weeks) thereafter (if clinically indicated). Latest pregnancy results (maximum 9 weeks old) must be available and reviewed by the treating physician or investigator prior to commencing a new cycle of infusion. A urine or serum pregnancy test is acceptable.
- k) For AEs/SAEs reported during screening, additional information such as medical history and concomitant medications may be needed.
- l) Post-treatment follow up: all patients will be followed up according to RECIST 1.1 every

Sponsor: Grupo Español de Tumores Neuroendocrinos y Endocrinos (GETNE)

12 weeks (+/-7 days) up to disease progression or death (whichever occurs first), regardless of the reason for ending the treatment. Neuroendocrine markers are to be analysed according to local practice. The follow-up period according to the protocol is 12 months considering last patient inclusion. Information on subsequent treatments should include the list of post-treatment therapies, the drugs administered, and the date of initiation and discontinuation of each drug. All the data will be recorded in the medical record and in the eCRF.

- m) The initial dose of atezolizumab will be administered before cabozantinib and must be administered over 60 minutes. If the first infusion is well tolerated, all subsequent infusions may be administered over 30 minutes. For the rest of the cycles, cabozantinib will be self-administered by the patients daily and as per principal investigator indications. Results for LTFs, electrolytes, and creatinine must be available before commencing an infusion (within 3 days) and reviewed by the treating physician or investigator prior to dosing.
- n) Biomarker study: Collection of the most recent archived tumour-biopsy sections. Processed blood samples at baseline, day 1 of cycle 2 (D1C2), at EOT/progression. Blood samples should be obtained in all patients at the time of EOT (even by toxicity without progressing) and samples are to be stored at site at -80 °C and are to be sent at the end of study (1 dry ice shipment per site).
- o) CT Scan or MRI is to be performed at baseline and q12w ± 1w until the confirmation of objective disease progression or death (whichever comes first). The schedule of q12w ± 1 week must be followed regardless of any delays in dosing, in case of suspected pseudo-progression; treatment should be continued until progression of disease is confirmed from the imaging results. RECIST assessments will be performed on images from CT scans (preferred) or MRI, each preferably with IV contrast of the neck, chest, abdomen (including liver and adrenal glands), and pelvis. Pelvic imaging is recommended only when primary or metastatic disease in the pelvic region is likely. Additional anatomy should be imaged based on signs and symptoms of individual patients at baseline and follow-up. Baseline assessments should be performed no more than 28 days before the date of inclusion and, ideally, should be performed as close as possible to and prior to the start of treatment. The confirmatory scans should be performed preferably at the next scheduled imaging visit and no less than 4 weeks after the prior assessment of PD (in the absence of clinically significant deterioration). If an unscheduled assessment was performed and the patient has not progressed, every attempt should be made to perform the subsequent assessment at the next scheduled visit.

1.4. STATISTICAL METHODS AND SAMPLE SIZE DETERMINATION

1.4.1. DETERMINATION OF SAMPLE SIZE

Simon-II optimal two-stage design was applied for sample size estimation. We hypothesise that the experimental therapy will improve the probability of expected objective response rate in refractory settings, from less than 5 % in previous reports, to 20 % in the current study. With 80 % of power (0.2) and unilateral alpha (0.1), 24 patients per cohort are needed to demonstrate the primary hypothesis. The Simon-II design suggested the observation of ≥ 1 patient with objective response within the first nine patients included in the first stage. If ≥ 1 out of nine patients in each cohort achieve an objective radiological response in the first stage, the study will continue to recruit 15 additional patients up to 24 patients per cohort. If ≥ 3 out of a total of 24 patients achieve a radiological objective response at the final analysis, the study should be declared positive. If stage I is reached only in one cohort, recruitment will continue in the successful cohort and stopped in the non-effective cohorts.

Sponsor: Grupo Español de Tumores Neuroendocrinos y Endocrinos (GETNE)

1.4.2. GENERAL CONSIDERATIONS

'Last patient last visit', as defined in the protocol, is 12 months after the enrolment of last patient. Subjects may continue to receive IMPs after the cut-off because treatment cannot be discontinued for ethical reasons, but in such cases, Sponsor agrees to continue with cabozantinib supply to sites to cover patient treatment until its finalisation and atezolizumab for a maximum of 6 months after the end of the study (LPLV). For these 6 additional months (since LPLV), the principal investigators must inform on any suspicion on adverse events/special situations in patients receiving atezolizumab's, to the marketing authorisation holder.

1.4.3. DESCRIPTION OF ANALYSIS SETS

Data will be analysed in the following populations:

1. Intent-To-Treat (ITT): All patients that has been enrolled in the trial.
2. Evaluable population per protocol (PP): All patients fulfilling all eligibility criteria without any protocol deviation that makes patient invalid for the primary endpoint evaluation.
3. Safety population: All patients receiving at least one dose of treatment.

1.4.4. MISSING DATA

The missing data will not be inputed and will be left as lost (missing value), however it will be presented. Missing data for drop-outs are not replaced by methods like LOCF (last option carried forward).

1.4.5. INTERIM ANALYSES AND DATA MONITORING

Interim analysis may be performed when analysing other primary endpoints.

1.5. SUMMARY OF STUDY DATA

For each categorical variable, the results will be summarised by frequencies and percentages. For each continuous variable, the results will be summarised by descriptive statistics such as median, range, and interquartile range or by means, standard deviations, and 95 % confidence intervals (CIs). For proportions, point estimates and exact 95 % confidence intervals will be calculated. For time to event endpoints, Kaplan-Meier estimates at selected time points and corresponding curves will be presented. Time to event is derived relative to the first study treatment administration. Laboratory values will be expressed as absolute values and in grades (ordinal categorical variables) according to NCI CTCAE v 5.0.

Treatment-emergent AE (AEs starting after the administration of study treatment and up to study completion) will be summarised by system organ class and preferred term. Grading will be presented by type and in tables showing the frequency and percentage of the within-patient worst grades. In addition, grade ≥ 3 AEs will be summarised separately. Full analysis details will be outlined in the statistical analysis plan (SAP).

Sponsor: Grupo Español de Tumores Neuroendocrinos y Endocrinos (GETNE)

Continuous data will be presented with the number of observations, mean value, standard deviation, minimum, maximum, and median. Categorical data will be presented as counts and percentages. Individual subject data will be listed.

Vital signs, ECG parameters, clinical laboratory data (haematology, serum biochemistry, and urinalysis) will be presented in tabular form. Values outside the reference range will be flagged, and the clinically significantly abnormal values will be listed in tabular form. Adverse events will be tabulated by system organ class and preferred term after medical coding using the according to NCI CTCAE v 5.0.

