6. ELIGIBILITY CRITERIA

6.1. INCLUSION CRITERIA

Patients eligible for inclusion in this study must meet all the following criteria:

1. Male or female subjects ≥ 18 years old.
2. Willingness to participate in the study by signing ICF approved by the trial Central Ethic Committee (CEIm).
3. Eastern Cooperative Oncology Group (ECOG) performance status of 0 or 1.
4. Measurable disease per RECIST 1.1 as determined by the investigator.
5. Patients with advanced and progressive neuroendocrine tumors histopathologically confirmed (as per local pathology report), meeting one of the following (according to WHO 2010 classification):
 - a. Cohort 1: Well-differentiated neuroendocrine tumours of the lung and thymus (WHO grade 1 and 2, typical and atypical carcinoids) after progression to somatostatin analogs, targeted agents, PRRT, and/or chemotherapy.
 - b. Cohort 2: Advanced anaplastic thyroid cancer in first-line or after progression to chemotherapy or investigational drugs, that underwent prior primary tumor surgical

resection or not. In patients that primary tumor has not been resected, the risk of aerodigestive compression or bleeding should be ruled out to ensure no interference with the administration of the investigational product and undesirable potential side effects related to the route of administration.

- c. Cohort 3: Adrenocortical carcinoma after progression to chemotherapy and/or mitotane.
- d. Cohort 4: Pheochromocytoma and paraganglioma after progression to peptide receptor radionuclide therapy (PRRT) if indicated. Prior chemotherapy and biological therapy, such as somatostatin analogs, are allowed.
- e. Cohort 5: Well-differentiated neuroendocrine tumours of digestive system (WHO grade 1 and 2) after progression to somatostatin analogs, targeted agents, PRRT, and/or chemotherapy.
- f. Cohort 6: Grade 3 neuroendocrine neoplasm (WHO grade 3, including NET and NEC G3) of any origin, excluding small cell lung cancer, after progression to chemotherapy or targeted agents/PRRT.

Note: Patients will be eligible for inclusion after progression to one of the lines aforementioned, without limit in the number of treatment lines.

6. Recovery from toxicity related to any prior treatments to \leq Grade 1, unless the AE(s) are clinically non-significant and/or stable on supportive therapy.

7. Ability to swallow tablets.

8. Adequate normal organ and marrow function as defined below:

- a. Haemoglobin \geq 9.0 g/dL.

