- j) Women of childbearing potential are required to have a pregnancy test within 72 hours prior to the first dose of the study drug, and every 3 cycles (9 weeks) thereafter (if clinically indicated). Latest pregnancy results (maximum 9 weeks old) must be available and reviewed by the treating physician or investigator prior to commencing a new cycle of infusion. A urine or serum pregnancy test is acceptable.
- k) For AEs/SAEs reported during screening, additional information such as medical history and concomitant medications may be needed.
- l) Post-treatment follow up: all patients will be followed up according to RECIST 1.1 every 12 weeks (+/-14 days) up to disease progression or death (whichever occurs first), regardless of the reason for ending the treatment. Follow up assessments may be performed q8w ± 2w if required by local standard clinical practice or by investigator criteria, as long as the frequency of assessments is maintained. Neuroendocrine markers are to be analysed according to local practice. The follow-up period according to this protocol is 12 months considering last patient inclusion. Information on subsequent treatments should include the list of post-treatment therapies, the drugs administered, and the date of initiation and discontinuation of each drug. All the data will be recorded in the medical record and in the eCRF.
- m) The initial dose of atezolizumab will be administered before cabozantinib and must be administered over 60 minutes. If the first infusion is well tolerated, all subsequent infusions may be administered over 30 minutes. For the rest of the cycles, cabozantinib will be self-administered by the patients daily and as per principal investigator indications. Results for LTFs, electrolytes, and creatinine must be available before commencing an infusion (within 3 days) and reviewed by the treating physician or investigator prior to dosing.
- n) Biomarker study: Collection of the most recent archived tumour-biopsy sections. Processed blood samples at baseline, day 1 of cycle 2 (D1C2), at EOT/progression. Blood samples should be obtained in all patients at the time of EOT (even by toxicity without progressing) and samples are to be stored at site at -80 °C and are to be sent at the end of study (1 dry ice shipment per site).

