9.2.1.1. Adverse Event (AE)

An AE is any untoward medical occurrence in a patient or clinical investigation subject administered a medicinal product and that does not necessarily have a causal relationship with this treatment. An AE can therefore be the development of a new medical condition, or the deterioration of a pre-existing medical condition. This includes any unfavorable and unintended sign (e.g. tachycardia, enlarged liver), symptom (e.g. nausea, chest pain) or the abnormal results of an investigation (e.g. laboratory findings, electrocardiogram) temporally associated with the use of a medicinal product, whether or not considered related.

This requirement includes specific events or symptoms associated with cancer progression or general clinical deterioration to ensure potential toxicities are not overlooked. Radiographic progression without associated clinical sequelae is not considered an AE; terms such as 'disease progression' should be avoided. Pre-existing medical conditions that worsen during a study will be recorded as AEs. Abnormal laboratory values, ECG findings, or vital signs are to be recorded as AEs if they meet the criteria described in Section 9.3.

All untoward events that occur after informed consent through 30 days (100 days for SAEs and AESIs) after the date of the decision to permanently discontinue study treatment (defined as the later of the date of the decision to discontinue all study treatment or the date of the last dose of any study treatment) are to be recorded by the investigational site.

At each scheduled and unscheduled visit, AEs are to be identified and assessed based upon study procedures, routine and symptom-directed clinical investigations, and subject query/report.

Assessment of the relationship of the AEs to study treatment by the investigator will be based on the following two definitions:

- Not Related: An event is assessed as not related to study treatment if it is attributable to another cause and/or there is no evidence to support a causal relationship.
- Related: An event is assessed as related to study treatment when there is a reasonable possibility that study treatment caused the event. Reasonable possibility means there is evidence to suggest a causal

relationship between study treatment and the event. This event is called a suspected adverse reaction. A suspected adverse reaction implies a lesser degree of certainty about causality than adverse reaction, which means any AE caused by a drug.

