9.6.2. Medication Errors/Overdose/Drug abuse/Drug misuse

Medication error is defined as accidental deviation in the administration of a drug (e.g. wrong dose administered, wrong dosing schedule, incorrect route of administration, wrong drug, expired drug administered). In some cases, a medication error may be intercepted prior to administration of the drug.

Any study medication overdose, misuse, abuse, or study medication error (excluding missed doses) that results in an AE or SAE requires reporting to the Sponsor or designee according to the guidance for AE and SAE reporting (Sections 9.1 and 9.2, respectively).

In case of overdose, the Coordinating Investigator or designee should be contacted promptly to discuss how to proceed. Any AEs that occur as a result of an overdose have to be treated according to clinical standard practice.

Please refer to the Investigator's Brochure for additional management recommendations for an overdose of cabozantinib and/or atezolizumab.

In addition, all study medication overdose, misuse, abuse or medication error, regardless of whether they result in an adverse event, should be recorded on the Adverse Event CRF

9.6.2 Lack of Efficacy or Worsening of study disease:

Events that are clearly consistent with the expected pattern of progression of the underlying disease should not be recorded as adverse events. These data will be captured as efficacy assessment data only. In most cases, the expected pattern of progression will be based on RECIST v1.1 criteria. In rare cases, the

determination of clinical progression will be based on symptomatic deterioration. However, every effort should be made to document progression through use of objective criteria. If there is any uncertainty as to whether an event is due to disease progression, it should be reported as an adverse event.

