2.6.9. SAE

Table 202. SAEs

Table 203. List of all SAEs

1: SAE reported in the period after signing the informed consent form and previous to the start of the study treatment.

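### The treatment-emergent AE rule looks only at start date, so an AE that begins before first dose and worsens on treatment can be left out, and the AE and SAE count tables do not say whether the rule applies to them

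*Combined protocol and SAP*

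**What the plan says.** SAP 1.5 defines the set to be summarised by system organ class and preferred term as "Treatment-emergent AE (AEs starting after the administration of study treatment and up to study completion". Protocol 10.6 has the same wording. Both then ask for worst grade within patient and a separate summary of grade 3 or higher AEs. SAP 1.5 refers the reader to the SAP for full details, so no later text adds to the rule.

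Collection starts earlier than dosing. Protocol 9.2.1.1 covers "All untoward events that occur after informed consent through 30 days (100 days for SAEs and AESIs", and footnote k to the schedule in 8.1 expects screening events: "For AEs/SAEs reported during screening, additional information such as medical history and concomitant medications may be needed". The synopsis says that the worst toxicity score is recorded. Inclusion criterion 6 admits residual toxicity up to Grade 1, or higher "unless the AE(s) are clinically non-significant and/or stable on supportive therapy".

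On worsening, protocol 9.2.1.1 says: "An AE can therefore be the development of a new medical condition, or the deterioration of a pre-existing medical condition". It adds: "Pre-existing medical conditions that worsen during a study will be recorded as AEs". It does not say what start date such a record carries.

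In SAP 2.6 (table numbers as in the body of the SAP), the rows and titles of Tables 190, 198 to 202, 206 and 210 to 213 read AE, AE of grade 3 or higher, or SAE. None is labelled treatment-emergent. The footnote to the SAE listing, Table 203, marks an "SAE reported in the period after signing the informed consent form and previous to the start of the study treatment".

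**The concern.** A treatment-emergent definition should separate what patients brought with them from what happened on treatment. A change in severity after dosing belongs to the second group, and an onset-only rule has no place for it when the event already had a record. The grade 3 or higher summary is where this shows most, because a mild screening event that becomes severe on treatment is exactly what that summary should capture.

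The table shells add a second uncertainty. If the AE and SAE tables are programmed from all records, they also take in events that were over before any dose was given. Two programmers could follow the same SAP and report different grade 3 or higher and SAE rates from the same data. Safety is a secondary objective, and these rates will be read as the profile of the combination.

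**Working it through.** The plan states no figure to reproduce. The check is to follow a few event types through the rule as written, through a table built from all recorded AEs, and through a rule with a worsening clause. The cases are hypothetical. All follow from collection from consent (protocol 9.2.1.1, footnote k in 8.1), recording of the worst grade (synopsis) and the onset-only rule (protocol 10.6, SAP 1.5).

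| Event | Onset-only rule | All recorded AEs | Onset or worsening |
|---|---|---|---|
| Starts in screening at Grade 1, reaches Grade 3 after dosing, one record | Left out | Counted, Grade 3 | Counted, Grade 3 |
| Same event, second record opened at worsening | Counted, Grade 3 | Counted, Grade 3 | Counted, Grade 3 |
| Medical-history condition worsens, AE dated at the worsening | Counted | Counted | Counted |
| Medical-history condition worsens, AE dated at original onset | Left out | Counted | Counted |
| Grade 3 AE starts in screening, does not worsen after dosing | Left out | Counted, Grade 3 | Left out |
| SAE between consent and first dose, resolved before dosing | Left out | Counted | Left out; kept in flagged listing |

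Under the onset-only rule, rows 1 and 2 are the same clinical event with different results, as are rows 3 and 4. The only difference is how the site completed the form. The protocol does not settle this. Sections 8.2.2 and 8.2.3 ask for new or worsening AEs at visits, but do not say whether worsening opens a new record.

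Rows 5 and 6 show the opposite problem if the tables take all records. The safety set (SAP 2.6) is defined by patient, as at least one dose, and puts no limit on event dates. The note to Table 200 takes each patient's highest reported grade, again with no post-dose limit.

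Scale of one reclassified patient, by simple division:

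- stage 1 cohort: 1/9 = 11.1%
- full cohort: 1/24 = 4.2%
- minimum total: 1/54 = 1.9%
- maximum total: 1/144 = 0.7%

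One patient can also move a term across a reporting threshold. Table 210 lists AEs above 20% with more than 4 patients. Applied within a cohort of 24, 5/24 = 20.8% is listed and 4/24 = 16.7% is not.

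These figures give the weight of a single patient. They do not estimate bias, because the documents do not give the number of patients with a pre-dose AE that worsens.

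**The case against.** Most toxicity carried in at entry is handled elsewhere. Protocol 8.2.1 puts clinically significant findings at the screening examination into medical history and records new ones after first dose as AEs. Section 9.2.1.1 makes the deterioration itself an AE. The natural reading is that such an AE begins when the deterioration begins, and it then meets the onset rule. This stands. It confines the clear exposure to AEs that start between consent and first dose, a window of normally up to 28 days, although footnote b in 8.1 lets consent come earlier. What remains for medical-history conditions is that the start date is left to the natural reading and not stated.

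The SAE listing is not at fault. SAEs are reported from consent (protocol 9.3.2), and Table 203 flags the pre-dose ones. A reader might infer that they inflate the SAE percentage. The documents do not say so: the footnote belongs to the listing and Table 202 carries none. Protocol 9.3.2 expressly requires the CRF page only for SAEs after treatment starts. The gap is that the SAP does not say which records Table 202 counts.

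Tables of treatment-related events are also largely protected from pre-dose records, since relatedness under 9.2.1.1 requires a reasonable possibility that study treatment caused the event.

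Finally, safety is summarised descriptively in a single-arm study, with no safety test in the SAP. This limits the consequence to the accuracy of the reported rates.

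**Conclusion.** The narrow point holds. The stated rule is onset-only, events are collected before dosing, and nothing guarantees that worsening after first dose produces a record with a post-dose start. The AE, grade 3 or higher and SAE count tables do not say whether the rule governs them. The size of the effect cannot be derived, and its direction depends on how the tables are built.

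Three stronger readings are tempting and should not be drawn:

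- **Both biases at once.** A reader might infer that grade 3 or higher rates are too low and SAE rates too high together. Within one table these exclude each other: a table limited by the onset rule cannot hold pre-dose events, and an unrestricted table does not lose the worsening event.
- **Size from the cabozantinib incidence figures.** Protocol 7.1.3 gives frequencies in treated patients. They are not prevalence at entry, and prior cabozantinib is an exclusion.
- **Harmless overdose or medication-error records counted as AEs.** Protocol 9.6.2 says that these, "regardless of whether they result in an adverse event, should be recorded on the Adverse Event CRF". That says where they are recorded. No text says they enter the AE counts.

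The conclusion assumes that at least some screening AEs are kept as single records. The documents allow this but do not establish it.

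**What to change.** In protocol 10.6 and SAP 1.5, define a treatment-emergent AE as one that starts on or after first dose, or was present before first dose and increases in CTCAE grade on or after it. Tabulate the worst post-dose grade.

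Apply this definition to Tables 190, 198 to 202, 206 and 210 to 213, and label them accordingly. Keep pre-dose SAEs in the flagged listing (Table 203) and leave them out of the percentages.

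State the recording convention the rule needs: either a new record at each increase in grade, or the grade at first dose and the date of any increase. A worst grade alone does not show whether it was reached before or after dosing.

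The cost is one sentence in each document, a short data-entry instruction and a little programming. Some rates may come out slightly less favourable. Design and patient care do not change.
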